Protocol Amendment Version 3 03/31/21			
03/31/21	Title Page	Update protocol version number and date for renewal submission	
03/31/21	Footer all pagers	Update version number and date	
03/31/21	Throughout protocol	Correct syntax/punctuation	
03/31/21	Study Coordinators	Remove [name], add [name]	
03/31/21	Schema	Revise to include patients who will receive other definitive therapy	
03/31/21	6.4.0 Inclusion Criteria/Exclusion Criteria	Revise to include patients who will receive other definitive therapy	
03/31/21	6.5.2 Patient Population	Revise to include patients who will receive other definitive therapy	
03/31/21	6.5.8 Safety & Clinical Follow-Up	Revise to include patients who will receive other definitive therapy	
03/31/21	6.12.0 Data Submission Schedule	Add Tissue Collection Form and submission schedule	
03/31/21	6.13 Study Calendar	Add tissue collection	

Renewal Version 3a Dated 10/12/2021

[figure not shown]
10/12/2021	Title Page	Update protocol version number and date for renewal submission	PRMC approved 11/02/2021 FDA Feb 2022
Amendment V4 02/15/2022			
02/15/2022	Title Page	Update protocol version number and date for submission	Oncore Updated Feb 15, 2022 FDA Feb 2022
	Title Page	Update Study team members (statistician, pathology, radiology team)	
	Footer all pagers	Update version number and date	
Renewal Version 4a 09/12/2022			
09/12/2022	Title Page	Update protocol version number and date for renewal submission	PRMC 10/11/2022 FDA 02/06/2023
	Footer all pagers	Update version number and date	
Renewal / Amendment Version 5 08/28/2023			
08/28/2023	Title Page	Update protocol version number and date for renewal submission Remove study coordinators	Pending PRMC Pending FDA
	Footer all pagers	Update version number and date Fix pagination error(s)	
	Formatting all pages	Document consistency fix spacing etc	
	Contents	Update table of Contents	
	6.5.3 PET Imaging	Clarify metabolites are collected whenever possible	
	6.13 Study Calendar		
	6.8.0 Risks and Benefits	Fix typographical error referencing PDAC &Clarify metabolites are collected whenever possible	

Contents

SCHEMA	6
6.1.0 Background	7
6.2.0 Objectives	10
6.3.0 Statement of Qualifications.....	10
6.4.0 Inclusion Criteria/ Exclusion Criteria.....	10
6.4.1 Inclusion of Women and Minorities	11
6.4.2 Registration Procedures & Screen Failures.....	11
6.5.0 METHODS	11
6.5.1 Study Design	11

6.1.0 Background

Chemokines, also known as chemoattractant cytokines, are a super family of small secreted proteins initially characterized by their ability to induce leukocyte migration. They are small proteins known as cytokines that have chemoattractant properties and, thus, are called chemokines. One of their most critical functions is governed by the specific amino acid sequence (or motif) of Glu-Leu-Arg (or ELR) immediately preceding the first cysteine of their CXC motif. ELR+ CXC chemokines are considered angiogenic, whereas ELRCXC chemokines are considered angiostatic¹. To date, more than 50 chemokines and 20 chemokine receptors have been identified. Chemokines and their receptors have a highly conserved sequence throughout the genetic tree². They are grouped into 4 distinct groups (C, CC, CXC, and CX3C), which are based on the number and position of conserved cysteine residues near the NH₂ terminus of the molecule³. The specific effects of the chemokines on their target cells are mediated by members of a family of 7-transmembrane-spanning, G-protein-coupled chemokine receptors. Most chemokines are able to bind with high affinity to multiple receptors while their receptors usually are restricted to a single subclass and induce an intensive signaling cascade of activated second messengers that lead to cell motility and multiple other functional effects in the target cells. Chemokines insert their cellular trafficking and processes are influenced significantly by chemokines via their receptors.

Chemokine Receptors: Most chemokine receptors bind specifically, but indiscriminately to their chemokine ligands. Chemokine receptors exist in many epithelial and hematopoietic cells. These receptors are members of the 7-TM GPCR super family. Like chemokines, chemokine receptors also share structurally conserved/homologous regions, which allow their subgrouping classification. In general, upon binding to their ligands, chemokine receptors undergo conformational changes that allow the binding of G proteins to intracellular loop epitopes and the carboxy terminal tail of the receptors³. The second intracellular loop of the receptors contains an Asp-Arg-Tyr-Leu-Ala-Ile-Val (DRYLAIV) motif, which is missing in the nonsignaling receptors and does not permit G-protein coupling². The chemokine receptors that do not bind to G proteins may act in synchrony with other proteins to support their effects. Examples of these alternative cohorts include b-arrestin, integrins, and growth factor receptors⁴⁻⁹.

Chemokines are vital for leukocyte migration and activation, and physiologically they have been implicated in various immune, inflammatory and activation responses such as allergic disease, atherosclerosis, and wound healing. Furthermore, chemokines play an important role in the neoplastic processes of many organs and in determining the location of the metastatic spread of cancer cells. For example in squamous cell carcinoma of head and neck, chemokine receptors orchestrate critical functions in oral tumorigenesis by favoring angiogenesis, tumor growth and metastasis^{10,11}. In prostate cancer, multiple chemokines and their receptors (including CCR5, CCR7, CCR9, CXCR1, CXCR2, CXCR3, CXCR4, CXCR5, CXCR7) are involved in the multistep process of metastasis^{5,8,12-15}. In cervical cancer, CXCR4 receptor has been shown to play an important role during cervical cancer invasion¹⁶. In addition, CXCR7 expression has been shown to predict poor disease-free and disease-specific survival in cervical cancer patients, and might be a promising new therapeutic marker. In a large majority of cases, CXCR7 is co-expressed with CXCR4 and/or EGFR, supporting the hypothesis that these receptors assist in CXCR7 signal transduction¹⁷. CXCR4 has been found to be upregulated in several other cancers such as breast, prostate, lung, bladder, ovarian, renal, oesophageal, colorectal, and pancreatic cancer, and lymphoma, melanoma, osteosarcoma, neuroblastoma, etc.¹⁸. In addition, high level of CXCR4 expression correlated with tumor progression and metastasis^{19,20}, as well as poor prognosis and resistance to chemotherapy^{21,22}. Thus, these receptors provide an important target for imaging and treatment of various types of cancers.

CCR2 in Head & Neck Cancer: The importance of chemokines and their cognate receptors in head and neck cancers is being revealed by increasing amount of studies. Recently, Version #5 08/28/2023

the expression of CXCR2 was reported substantially higher than that in paraneoplastic tissue in laryngeal squamous cell carcinoma²³. Elevated expression was significantly related with lymph node metastasis, histological grade, and 5-year survival²³. Thus, CXCR2 expression could be considered as a potent prognostic marker for laryngeal squamous cell carcinoma patients²³. Several studies have also documented the significance of CXCR4 in HNSCC tumor progression and organ-specific metastasis^{24,25}. Wang et al investigated the expression of CXCR4 in nasopharyngeal carcinoma tissues, and they found that CXCR4 expression was elevated in tumor tissues and the increased expression was correlated with metastatic rates in patients as well as poor overall survival²⁶. This finding was consistent with another study which reported that CXCR4 mRNA was significantly higher in HNSCC tissues than in paraneoplastic tissues and its expression were associated with lymph node metastasis and distant metastasis²⁷. These findings clearly demonstrate that CXCR4 could also be used to predict prognosis and metastasis in HNSCC patients.

Chen et al. reported that a 64I mutation of the CC chemokine receptor-2 (CCR2) is significantly associated with oral cancer susceptibility²⁸. Also, another group demonstrated that mutation of MCP-1 gene, which encodes CCR2 ligands, increased the expression of MCP-1 resulting in elevated CCR2 activity which could increase the risk for developing oral squamous carcinoma²⁹. The authors predicted that MCP-1 and CCR2 could be used as genetic markers for diagnosis of oral carcinoma squamous²⁹. In addition, Fujita et al. found that The CCL2-CCR2 axis is associated with lymphatic metastasis in oral squamous cell carcinoma³⁰. Yang et al. have shown that CCL2-CCR2 axis could promote nasopharyngeal carcinoma (metastasis by activating ERK1/2-MMP2/9 pathway. This study helps to develop novel therapeutic targets for distant metastasis in nasopharyngeal carcinoma³¹. Another CC chemokine receptor, i.e., CCR7, which plays a critical role in the migration of activated dendritic cells to regional lymph nodes, was also found elevated in HNSCC tumor tissues compared with paraneoplastic tissues and the elevated expression of CCR7 was correlated with lymph metastasis and tumor tissue differentiation status²⁷. Another study evaluated the expression of CCR7 in primary and metastatic tumor cell lines and biopsies from both primary and metastatic lesions, and it was found that CCR7 expression was elevated in metastatic cells and tissues²⁷. These findings reveal an important role of CCR7 in mediating the metastasis and tumor malignancy in head and neck squamous cell cancer patients. Taken together, accumulating evidence indicates that the altered expressions of various chemokine receptors (and their cognate ligands as well) in head and neck squamous cell cancer are associated with different cellular events including cell survival, tumor progression, and metastasis. The expression of chemokine receptors is associated with tumor cell differentiation and prognosis of head and neck squamous cell cancer patients. Moreover, their expression is also, to some degree, histologically specific, i.e., the expression of these chemokine receptors indicates it is the squamous cell carcinoma rather than other types (such as adenoid cystic carcinoma)³². These features, along with other tumor biomarkers, may help oncologists to assess their patients more thoroughly

In the last few decades, human papillomavirus (HPV) has emerged as the key etiologic factor driving the rising incidence of oropharyngeal squamous cell cancer^{33, 34}. HPV-related oropharyngeal squamous cell cancer has emerged as a distinct clinical entity of head and neck cancer with expected high survival. This recognition has led to the investigation of whether a population of patients can be identified who can safely undergo treatment de-escalation, in an effort to minimize long-term treatment toxicity while maintaining excellent survival. The relationship of HPV and CCR2 has not been established in head and neck cancer. As the number of patients in this study is limited and we often do not know the HPV status of the patients, it will be extremely important to assess the CCR2 expression in the cancer tissues of HPV+ and HPV- patients to understand better the relationship of CCR2 expression and HPV. In future studies, we will be able to assess whether presence of CCR2 in each group is predictive of worse prognosis

and more aggressive therapy is needed. This will be very important as treatment deintensification for HPV+ squamous cell cancer of head and neck cancer is being evaluated.

Positron Emission Tomography (PET) Using CCR-Based Tracers: PET imaging of tumor metabolism has been extensively used for staging, treatment planning and monitoring of response in various types of malignancies. Due to the importance of chemokine receptors, attention has been made to develop radiolabeled compounds that targets these receptors.

^{64}Cu -DOTA-ECL1i-PET/CT:

Our group has developed a CCR2 specific PET radiotracer based on the peptide, ECL1i (d(LGTFLKC)) and radiolabeled with ^{64}Cu (^{64}Cu -DOTA-ECL1i)³⁵. The CCR2 detection sensitivity and specificity has been demonstrated in multiple preclinical studies and ex vivo human tissues³⁶⁻³⁸. We have tested this tracer in preclinical inflammation models, human pancreatic cancer and human head and neck cancer and demonstrated a positive correlation between the PET signals and CCR2 expression.

[figure not shown]

Figure 1. *Ex vivo* characterization of ^{64}Cu -DOTA-ECL1i binding to CCR2 in human head and neck cancer tissue. (A) H&E. (B) CCR2 DAB staining showed high expression of the receptor in the area full of tumor cells. Control IgG staining confirmed the receptor staining specificity. (C) Autoradiography showed tracer binding to the cancerous area of the tissue and the specificity was verified by the blocking. (D) Quantitative comparison of counts in binding and blocking tissues.

receptors on tumor cells (Figure 1C). The competitive receptor blocking using non-radiolabeled DOTA-ECL1i conjugate in excess amount (DOTA-ECL1i: ^{64}Cu -DOTA-ECL1i molar ratio = 100:1) significantly blocked the binding to the tissue. Quantitative comparison of counts in binding and blocking tissues demonstrated $50.8 \pm 0.6\%$ ($n=4$, $p<0.005$) blocking efficiency (Binding was set as 1 for each specimen), confirming the binding specificity (Figure 1D).

Ex vivo characterization of ^{64}Cu -DOTA-ECL1i binding to CCR2 expressed in human head and neck cancer tissue: CCR2 immunohistochemistry was performed on the de-identified human cancerous tonsil tissue collected from the SCCTPC (Figure 1A). As shown in Figure 1B, strong CCR2 (brown color) signals were detected in the area of tumor cells. Low CCR2 signals were also measured in the muscle and soft tissue, likely due to the expression of the receptors on the infiltrated macrophages or inflammatory cells. The control IgG staining showed negative signal of CCR2, confirming the specific expression of CCR2 on these tumor cells. The *ex vivo* binding assay of ^{64}Cu -DOTA-ECL1i using autoradiography showed strong binding to the cancerous area with signals in similar profile to the CCR2 IHC, indicating the specific binding of the tracer to the CCR2

Summary: CCR2 is a significant prognostic biomarker in head and neck cancer. Currently there is no clinical biomarker to study CCR2, its prognostic significance or to select patients for CCR2-targeted therapy and to monitor response to such therapy. Our group has developed a CCR2 specific PET radiotracer based on the peptide, ECL1i (d(LGTFLKC)) and radiolabeled with ^{64}Cu (^{64}Cu -DOTA-ECL1i). We also have found that ^{64}Cu -DOTA-ECL1i specific binding has been demonstrated in human head and neck cancer tissue. Currently ^{64}Cu -DOTA-ECL1i is being studied in several clinical settings under IND (#137620) at Washington University. Our group is studying ^{64}Cu -DOTA-ECL1i in patients with head and neck cancer. The use of ^{64}Cu -DOTA-ECL1i has proven to be safe in our ongoing clinical trials with favorable radiation dosimetry (0.064 rem/ mCi) and is compatible with other imaging tracers such as ^{18}F -Fludeoxyglucose (FDG)

6.2.0 Objectives

We are planning to perform a trial with goals to evaluate tumor uptake of ^{64}Cu -DOTA-ECL1i in patients with squamous cell head and neck cancer with at least one measurable lesion of ≥ 1.5 cm. We also will correlate the tumor uptake of ^{64}Cu -DOTA-ECL1i with immunohistochemical staining for CCR2 receptors in the tumor specimens.

Study objectives:

- 6.2.1 To determine the diagnostic quality and CCR2 expression detection rate of ^{64}Cu -DOTA-ECL1i-PET/CT images.
- 6.2.2 To evaluate the relationship between ^{64}Cu -DOTA-ECL1i uptake and immunohistochemical staining for various types of chemokine receptors such as CCR2.
- 6.2.3 To assess the association of CCR2 expression and HPV status. CCR2 immunohistochemical staining in HPV+ and HPV- squamous cell cancer of the head and neck. To better assess the analysis of tissue prospectively we will retrospectively review a limited number of identified samples obtained from the Department of Pathology at Washington University (20 total samples).

6.3.0 Statement of Qualifications

The study will be done under eIND (#137620). [name]., Washington University School of Medicine, St. Louis, Missouri is the physician-investigator of the IND.

6.4.0 Inclusion Criteria/ Exclusion Criteria

Adult patients (men or women) with confirmed new diagnosis of squamous cell head and neck cancer who are being evaluated for surgical resection or definitive therapy are eligible to participate in this study.

Inclusion Criteria:

- Adult patient 18 years of age or older
- Cytology or biopsy-proven squamous cell head and neck cancer scheduled to be treated with standard of care surgery. Patients who are not surgical candidates should have adequate tissue from tumor biopsy for analysis of CCR2.
- Lesion size of at least 1.5 cm (treatment naïve)
- Able to give informed consent
- Not currently pregnant or nursing: Subject must be surgically sterile (has had a documented bilateral oophorectomy and/or documented hysterectomy), post-menopausal (cessation of menses for more than 1 year), non-lactating, or of

childbearing potential for whom a urine pregnancy test (with the test performed within the 24 hour period immediately prior to administration of ^{64}Cu -DOTA-ECL1i is negative

Exclusion Criteria:

- Patients with other invasive malignancies, with the exception of non-melanoma skin cancer, who had (or have) any evidence of the other cancer present within the last 2 years
- Unable to tolerate approximately 90 min (total time) of PET/CT imaging.

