6.5.3.1 PET Imaging Procedure

Following administration of 8-10 mCi of the radiotracer ⁶⁴Cu-DOTA-ECL1i-PET/CT, all twenty subjects who enter on study will undergo a 60 minute dynamic scan centered over the site of the known tumor. An additional limited scan (top of head to upper/mid-chest) will be performed approximately 1-3 hours after administration.

For dynamic imaging, the subject will be placed supine on the imaging table with arms secured comfortably by the side of the body. A low dose spiral CT scan for attenuation correction will be obtained centered on the primary tumor site. The CT will consist of a 5-20 second topogram for determining correct anatomical positioning followed by a spiral CT at a maximum of 50 mAs. Care dose will be calculated for each scan and the care dose imaging parameters will be used if less than the maximum 50 mAs is calculated. CT imaging will be acquired with a standard 120 kVp. Average spiral CT scan time is 5-30 seconds. Scans are acquired

using a 3-5 mm slice thickness. Immediately after the attenuation CT scan, subjects will be injected with 8 – 10 mCi ^{64}Cu -DOTA-ECL1i. The dose will be followed with a normal saline flush of 10-30 ml. A 60 min list mode dynamic imaging acquisition will follow study drug injection. At the end of the imaging session, subjects will be encouraged to void.

Subjects will be allowed to rest outside of the scanner until such time subject indicates they are willing to start the 2nd scan (1 – 3 hours post injection). Scan #2 will consist of a limited body scan from the vertex to upper/mid chest region. Following topogram and low dose CT scan for attenuation correction (maximum 50 mAs with care dose imaging parameters) a 2 bed limited scan from vertex to upper / mid chest will be obtained at 3-5 minutes per bed position.

To add to the existing safety profile of ^{64}Cu -DOTA-ECL1i, all subjects will undergo vital sign measurement, clinical laboratory testing, and ECG testing as specified in sections 6.5.5, 6.5.6 and 6.5.7 of the protocol.

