6.5.6 Clinical Laboratory Testing

Laboratory tests will consist of the following: standard CBC, and comprehensive metabolic panel obtained at the following time points:

- Baseline: Baseline labs may be obtained anytime within 21 days or immediately prior to ^{64}Cu -DOTA-ECL1i injection and can be done as standard of care or for research purposes.
- Discharge: At least 60 minutes post injection or prior to study discharge.

Approximately 15 mL of blood will be collected for clinical laboratory testing, serum stability / metabolite analysis.

Labs obtained at baseline prior to injection of ^{64}Cu -DOTA-ECL1i will be compared to labs obtained at study discharge. The following changes from baseline clinical laboratory values are considered to be noteworthy and require assessment as to clinical significance when they fall outside of normal limits. Clinically significant changes in laboratory values which are attributed to ^{64}Cu -DOTA-ECL1i injection should be followed up until they return to baseline or normal levels, or until follow-up is no longer warranted. Laboratory values that are abnormal at baseline but move into normal range will not be considered clinically significant. If a clinically significant change of a laboratory value is noted, it will be reported on the PI Data Safety and Review Form so that the PI can assess the change as being attributable to ^{64}Cu -DOTA-ECL1i injection. All clinically significant laboratory changes as identified below

which are identified by the PI as being attributable to ^{64}Cu -DOTA-ECL1i will be recorded on the adverse event log.

Clinically Significant Laboratory Values

Analyte	Change from baseline
Hemoglobin	> 2g/dL
WBCs	> 1 K/mm ³
Neutrophils	> 10 %
Lymphocytes	> 10%
Platelets	> 50 K/mm ³
Creatinine	> 0.75 mg/dL
BUN	> 20 mg/dL
Calcium	> 1mg/dL
Sodium	> 5 mmol/L
Potassium	> 0.5 mmol/L
CO ₂	> 4 mmol/L
ALT (SGPT)	> 150 IU/L
AST (SGOT)	> 100 IU/L
Alkaline Phosphatase	> 150 IU/L
Total Bilirubin	> 0.5 mg/dL
Albumin	> 1g/dL

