6.12.0 Data Submission Schedule

Case report forms with appropriate source documentation will be completed according to the schedule listed in this section.

Case Report Form	Submission Schedule
Eligibility check List	Prior to registration
Original Consent Form	Prior to registration
PET Imaging Form	Real Time completion of events as they occur
PET Imaging Follow up Form	Real time to comply with protocol requirements
Adverse Event Log	After follow up has been completed
PI Data Safety Review	After follow up and AE forms have been completed
Tissue Collection Form	At time of surgery or requested after follow up from standard of care biopsy sample
Image Analysis Form	Per PI Schedule

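### The pregnancy criterion in 6.4.0 is misworded: non-lactating stands as its own alternative, so read literally a non-nursing woman of childbearing potential qualifies without the urine test that is plainly intended

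*Combined protocol and SAP*

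**What the plan says.** Section 6.4.0 covers pregnancy in one inclusion criterion. It opens "Not currently pregnant or nursing: Subject must be surgically sterile" and continues with the alternatives "post-menopausal (cessation of menses for more than 1 year), non-lactating, or of" and then "childbearing potential for whom a urine pregnancy test (with the test performed within the 24 hour period immediately prior to administration", ending with the requirement that the result be negative. The list therefore has four items separated by commas and closed by *or*: surgically sterile; post-menopausal; non-lactating; of childbearing potential with a negative test.

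The sections that describe the imaging day do not mention the test. Section 6.5.3.1 says "Immediately after the attenuation CT scan, subjects will be injected with" the tracer, and for safety data it states that "all subjects will undergo vital sign measurement, clinical laboratory testing, and ECG testing as specified in sections 6.5.5, 6.5.6 and 6.5.7". Section 6.5.6 defines the laboratory work: "Laboratory tests will consist of the following: standard CBC, and comprehensive metabolic panel obtained at the following time points". The 6.13 calendar has rows for blood, vital signs and ECG, and its footnote (a) gives the baseline windows for these (about 30 minutes for vital signs and ECG, 21 days for blood). It has no row or footnote for a pregnancy test.

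Section 6.4.2 has an investigator sign an eligibility checklist. Section 6.12.0 lists the "Eligibility check List" as due before registration and the PET Imaging Form as completed in real time. The contents of neither form are shown.

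**The concern.** Not nursing belongs with not pregnant, as a condition that applies whichever reproductive category a woman falls in. Placed inside an *or* list, it becomes sufficient on its own. The woman for whom the test was written, who could be pregnant without knowing it, can then satisfy the list by not nursing. The lead-in excludes a known pregnancy but does not itself call for a test.

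At stake is avoidable exposure of an unrecognised pregnancy to the tracer and two CT scans. Section 6.8.0 puts the participant's total at 0.91 rem with a 10 mCi injection, and says participants will not benefit directly. A safeguard for a non-therapeutic exposure should have one reading, and it should be visible to the staff who carry it out. The question concerns participant safety only and does not touch any estimate or test in section 6.7.0.

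**Working it through.** No sample-size or power calculation applies. The check compares the criterion as written with the criterion as evidently meant.

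**Terms, all from 6.4.0.** L = lead-in (not pregnant and not nursing). S = surgically sterile. P = post-menopausal. N = non-lactating. C = of childbearing potential. T = negative urine test within 24 hours before administration.

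**As written:** L AND [S OR P OR N OR (C AND T)].

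L already contains not nursing, so anyone who satisfies L also satisfies N, and the bracket is then always true. The rule collapses to L alone, and S, P and the test clause do no work. This shows two things: the test is not compelled by the literal text, and the literal text cannot be what was meant, because three of the four items would be pointless.

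**As meant:** L AND [S OR P OR (C AND T)].

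**Women of childbearing potential.** Nursing (yes, no) crossed with test (none, negative, positive) gives 2 × 3 = 6 states. A positive test is taken as pregnancy, and an untested woman as not known to be pregnant.

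| State | As written | As meant |
|---|---|---|
| Nursing, any test status (3 states) | fails L | fails L |
| Not nursing, positive | fails L | fails L |
| Not nursing, negative | passes | passes |
| Not nursing, no test | **passes** | **fails** |

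The written rule passes 2 states and the intended rule passes 1. The single difference is the non-nursing, untested woman. This count compares wordings and does not measure risk.

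**Other women.** Sterile or post-menopausal women pass both versions if not pregnant and not nursing, and fail both through L otherwise. Nothing changes for them.

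**Men.** Section 6.4.1 makes men eligible, but the criterion speaks of the subject. As written, the only list item that readily fits a man is N. If N is simply removed, no item fits him. The reworded criterion must therefore be limited to female subjects.

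**Whether another section closes the gap.** Sections 6.5.3.1 and 6.13 are the two natural places for a reminder, and neither names the test. Section 6.5.6 is confined to blood count and metabolic panel. The eligibility checklist or the PET Imaging Form may carry the test, but their contents cannot be seen.

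**The case against.** The strongest reply is that nobody would act on the literal reading. To skip the test, staff would have to pass over the clause written for exactly this woman and rely on a word that only repeats the lead-in. A reasonable coordinator would test. This stands, and it is why the point is a wording correction.

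A second reply is that an inclusion criterion binds without being repeated, and that 6.4.0 already runs the 24-hour window up to administration and not to registration. This also stands. The absence of the test from the calendar leaves no requirement unstated. The sections on vital signs, ECG and safety laboratory work would not be expected to name a one-time eligibility test, so their silence carries no weight.

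A third reply is that the checklist, the imaging form and the consent text are not available here and may include the test. That is possible, and no inference about actual practice is drawn from their absence.

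Two stronger readings are tempting. A reader might infer that the protocol allows a woman with a positive test to be scanned; the lead-in excludes her. A reader might also infer that the protocol has no pregnancy-test requirement, or no timing for it; the childbearing-potential clause supplies both. What survives the objections is that the sentence setting the rule, taken literally, does not compel the test.

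**Conclusion.** The criterion is wrong as written, and the consequence is minor. *Non-lactating* is placed as an alternative where a joint condition was meant. Followed literally, the rule admits a non-nursing woman of childbearing potential who has not been tested. The intent to require a negative result within 24 hours before administration is clear from the same sentence.

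The size of the problem cannot be stated. The documents give no age or sex mix for the 20 planned subjects and no fetal dose, so neither the number of women affected nor the harm to a fetus can be estimated. The situation is expected to be infrequent. Sample size, endpoints and analysis do not change.

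The conclusion rests on reading the commas and the closing *or* in their ordinary sense, and on the available sections being the whole of the operative text. It does not support a claim that participants have been or will be imaged untested. The calendar entry is a matter of operational consistency and not a second defect.

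**What to change.** Reword the criterion in 6.4.0 along these lines:

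*Female subjects must be not pregnant and not nursing, AND must meet one of the following: (a) surgically sterile; (b) post-menopausal; (c) of childbearing potential with a negative urine pregnancy test within 24 hours before injection of the tracer.*

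The existing definitions of surgical sterility and menopause can be kept in (a) and (b).

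In the 6.13 calendar, add the test as a pre-injection item for women of childbearing potential, with its 24-hour window in footnote (a) beside the windows already given there.

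The cost is one reworded criterion, one calendar row and one footnote phrase, which can go into the next amendment. No new procedure is created, because 6.4.0 already calls for the test.
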